5.1.1 Retesting During Screening or Lead-in Period

Retesting of laboratory parameters and/or other assessments during the Screening or Lead-in period will not be permitted (this does not include parameters that require a confirmatory result) unless there was a technical error in performance of the lab test and the first result is invalid.

Any new result will override the previous result (ie, the most current result prior to dosing) and is the value by which study inclusion will be assessed, as it represents the subject's most current, clinical state.

5.2 Study Materials

- NCI CTCAE version 4.0
- Nivolumab Investigator Brochure
- Ipilimumab Investigator Brochure
- Pharmacy Binder
- Laboratory manuals for collection and handling of blood (including biomarker) and tissue specimens
- Site manual for operation of interactive voice response system, including enrollment worksheets
- Pregnancy Surveillance Forms
- RECIST 1.1 pocket guide
- CA209204 Imaging Manual

5.3 Safety Assessments

5.3.1 Medical History, Physical Exam, Physical Measurements

At baseline, a medical history will be obtained to capture relevant underlying conditions. The baseline examinations should include weight, height, ECOG Performance Status, blood pressure (BP), heart rate (HR), temperature, and oxygen saturation by pulse oximetry at rest (also monitor amount of supplemental oxygen if applicable) should be performed within 28 days prior to first dose.

Baseline local laboratory assessments should be done within 14 day prior to first dose and are to include: CBC w/differential, Chemistry panel including: LDH, AST, ALT, ALP, T.Bili, BUN or serum urea level, creatinine, Ca, Mg, Na, K, Cl, Glucose, amylase, lipase, TSH, Free T4, Free T3, Hep B/C (HBV sAG, HCV antibody, or HCV RNA).

While on-study and during follow-up, local laboratory assessments are to be conducted as specified on [Table 5.1-2](#) to [Table 5.1-4](#). Thyroid function testing is to be done every 6 weeks (every 3 cycles) for subjects receiving nivolumab.

Subjects will be evaluated for safety if they have received any study drug. Toxicity assessments will be continuous during the treatment phase. During study treatment and nivolumab Follow-Up Visits 1 and 2, toxicity assessments should be done in person. Once subjects reach the survival follow-up, either in-person visits or documented telephone calls/email correspondence to assess the subject's status are acceptable.

Adverse events and laboratory values will be graded according to the NCI-CTCAE version 4.0.

Oxygen saturation by pulse oximetry at rest (also monitor amount of supplemental oxygen if applicable) should be assessed at each on-study visit prior to dosing. The start and stop time of the study therapy infusions should be documented.

Physical examinations are to be performed as specified in [Section 5.1](#) and as clinically indicated. If there are any new or worsening clinically significant changes since the last exam, report changes on the appropriate non-serious or serious adverse event page.

On treatment local laboratory assessments are to be completed within 72 hours prior to dosing.

Additional measures, including non-study required laboratory tests, should be performed as clinically indicated or to comply with local regulations. Laboratory toxicities (eg, suspected drug induced liver enzyme evaluations) will be monitored during the follow-up phase via on site/local labs until all study drug related toxicities resolve, return to baseline, or are deemed irreversible.

If a subject shows changes on pulse oximetry or other pulmonary-related signs (hypoxia, fever) or symptoms (eg, dyspnea, cough, fever) consistent with possible pulmonary-related signs (hypoxia, fever) or symptoms (eg, dyspnea, cough, fever) consistent with possible pulmonary adverse events, the subject should be immediately evaluated to rule out pulmonary toxicity, according to the suspected pulmonary toxicity management algorithm in the BMS-936558 (nivolumab) IB.

Some of the assessments referred to in this section may not be captured as data in the eCRF. They are intended to be used as safety monitoring by the treating physician. Additional testing or assessments may be performed as clinically necessary or where required by institutional or local regulations.

5.3.2 Vital Signs

Vital signs consist of blood pressure, heart rate, respiratory rate and temperature measurements. Vital signs will be obtained as outlined in [Table 5.1-1](#) to [Table 5.1-3](#).

5.3.3 Imaging Assessment for the Study

All subjects will undergo CT scanning and volumetric MRI of the brain at the time points specified in [Table 5.1-1](#) to [Table 5.1-4](#).

CT and MRI scans will be assessed locally per the modified RECIST 1.1 criteria outlined in [Appendix 3](#). Up to 5 extracranial and 5 intracranial lesions will be followed for efficacy per the criteria. Please refer to [Appendix 3](#) for guidelines regarding images, target lesion selection and response criteria.

Any incidental findings of potential clinical relevance that are not directly associated with the objectives of the protocol should be evaluated and handled by the Study Investigator as per standard medical/clinical judgment.

Clinically significant radiologic findings or changes from baseline scans will be coded as adverse events or serious adverse events according to the criteria described in [Section 6](#).

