1.3.2 Secondary Objectives

- To assess the extracranial clinical benefit rate defined as CR+PR+SD > 6 months (per RECIST 1.1 criteria)
- To assess intracranial objective response rate (ORR), intracranial progression-free survival (PFS) per modified RECIST 1.1 criteria
- To assess extracranial ORR, extracranial PFS per RECIST 1.1 criteria
- To assess global CBR, global ORR, global PFS per a combination of modified RECIST 1.1 criteria for intracranial lesions and RECIST 1.1 for extracranial disease
- To assess OS
- To evaluate the intracranial-specific safety and tolerability of the combination regimen in patients with or without stereotactic radiotherapy (SRT) received prior to study entry, or while on study.

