All patients will be treated with the combination regimen of nivolumab 1 mg/kg combined with ipilimumab 3 mg/kg Q3W (4 doses), followed by nivolumab monotherapy (3 mg/kg Q2W) for a maximum of 24 months, or until disease progression or unacceptable toxicity. The use of SRT (single episode) for disease progression for ≤ 3 intracranial lesions is permitted. (Section 3.4.2.2) Recommended intervals between treatment with study drug and use of SRT, dose delay after SRT, allowable steroid use (≤ 16 mg dexamethasone PO QD), and tapered over no more than 4 weeks), and observation of patients post SRT when treatment is resumed are also specified in Section 3.4.2.2. Any subject who meets criteria for discontinuation following SRT (Section 4.5.5) will proceed to follow-up for safety, progression, and overall survival after discontinuation of study medication based on the assessment schedules presented in Section 5. NOTE: To continue on-study after SRT, at least 1 non-irradiated target lesion must remain after SRT treatment.

A follow-up period of 3 years from the date of first treatment with study drugs is available for all subjects. The study will close after the last enrolled subject completes 3 years of follow up from

the date of first treatment or the study is discontinued by the Sponsor. The study design is presented in [Figure 3.1-1](#):

Figure 3.1-1: CA209204 Study Design

- Subjects may continue to receive treatment for a maximum of 24 months, or until confirmed progression or unacceptable toxicity. After discontinuation from treatment with study drug(s) subjects will proceed to follow-up. Subjects who continue to respond at the end of on study treatment may be prescribed study medication through commercial supply or appropriate care per investigator.
- Use of SRT for progression of ≤ 3 intracranial lesions will be allowed per protocol-specific guidelines (See Section 3.4.2.2). Subjects who require SRT after second episode of disease progression will be discontinued from treatment and proceed to follow-up.
- All subjects who are discontinued from treatment with study drug(s) will proceed to follow-up. See Table 5.1-4 for schedule of follow up assessments.

SRT = stereotactic radiotherapy

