6 ADVERSE EVENTS

An *Adverse Event (AE)* is defined as any new untoward medical occurrence or worsening of a preexisting medical condition in a clinical investigation subject administered study drug and that does not necessarily have a causal relationship with this treatment. An AE can therefore be any unfavorable and unintended sign (such as an abnormal laboratory finding), symptom, or disease temporally associated with the use of study drug, whether or not considered related to the study drug.

The causal relationship to study drug is determined by a physician and should be used to assess all adverse events (AE). The causal relationship can be one of the following:

Related: There is a reasonable causal relationship between study drug administration and the AE.

Not related: There is not a reasonable causal relationship between study drug administration and the AE.

The term "reasonable causal relationship" means there is evidence to suggest a causal relationship.

Adverse events can be spontaneously reported or elicited during open-ended questioning, examination, or evaluation of a subject. (In order to prevent reporting bias, subjects should not be questioned regarding the specific occurrence of one or more AEs.)

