6.1 Serious Adverse Events

A *Serious Adverse Event (SAE)* is any untoward medical occurrence that at any dose:

- results in death

- is life-threatening (defined as an event in which the subject was at risk of death at the time of the event; it does not refer to an event which hypothetically might have caused death if it were more severe)
- requires inpatient hospitalization or causes prolongation of existing hospitalization (see **NOTE** below)
- results in persistent or significant disability/incapacity
- is a congenital anomaly/birth defect
- is an important medical event (defined as a medical event(s) that may not be immediately life-threatening or result in death or hospitalization but, based upon appropriate medical and scientific judgment, may jeopardize the subject or may require intervention [eg, medical, surgical] to prevent one of the other serious outcomes listed in the definition above.) Examples of such events include, but are not limited to, intensive treatment in an emergency room or at home for allergic bronchospasm; blood dyscrasias or convulsions that do not result in hospitalization.) Potential drug induced liver injury (DILI) is also considered an important medical event. (See [Section 6.6](#) for the definition of potential DILI.)

Suspected transmission of an infectious agent (eg, pathogenic or nonpathogenic) via the study drug is an SAE.

Although pregnancy, overdose, cancer, and potential drug induced liver injury (DILI) are not always serious by regulatory definition, these events must be handled as SAEs. (See [Section 6.1.1](#) for reporting pregnancies).

NOTE:

The following hospitalizations are not considered SAEs in BMS clinical studies:

- a visit to the emergency room or other hospital department < 24 hours, that does not result in admission (unless considered an important medical or life-threatening event)
- elective surgery, planned prior to signing consent
- admissions as per protocol for a planned medical/surgical procedure
- routine health assessment requiring admission for baseline/trending of health status (eg, routine colonoscopy)
- medical/surgical admission other than to remedy ill health and planned prior to entry into the study. Appropriate documentation is required in these cases

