7.6.5 Adverse Events

AEs will be summarized for all treated subjects and by cohorts and by SRT status. The following analyses will be conducted:

- Overall summary of any AEs by worst CTC grade (grade 1, 2, 3, 4, 5, unknown) presented by SOC/PT
- Overall summary of any non-serious AEs presented by SOC/PT. This table will be restricted to events with an incidence greater or equal to 5% in all treated subjects.
- Overall summary of any AEs by worst CTC grade (any grade, grade 3-4, grade 5) presented by SOC/PT. This table will be restricted to events with an incidence greater or equal to 5% in all treated subjects.
- Overall summary of drug-related AEs by worst CTC grade (any grade, grade 3-4, grade 5) presented by SOC/PT
- Overall summary of any AEs that required immune modulating medication by worst CTC grade (any grade, grade 3-4, grade 5) presented by SOC/PT.

The analyses will be conducted using the 30 days as well as 100 days extended safety window.

In addition, overall summary of late-emergent drug-related AEs (defined as drug-related events reported beyond 100 days after last dose of study therapy) by worst CTC grade (grade 1, 2, 3, 4, 5, unknown) will be presented by SOC/PT.

By-subject AE listing and by-subject listing of any AE requiring immune modulating medications will be provided for all treated subjects.

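### Tumor progression is not exempted from AE coding of scan changes, so all-causality AE and SAE totals by on-study SRT status are partly fixed by how the SRT group is selected

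*Protocol*

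**What the plan says.** Protocol Section 5.3.3 covers the CT and brain MRI scans on which lesions are followed for efficacy. It leaves incidental findings unrelated to the objectives to clinical judgment, then states: "Clinically significant radiologic findings or changes from baseline scans will be coded as adverse events or serious adverse events". Section 6 supplies the criteria for this coding.

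Section 6 defines an adverse event as "any new untoward medical occurrence or worsening of a preexisting medical condition in a clinical investigation subject administered study drug", and includes signs, symptoms or disease "whether or not considered related to the study drug". The exceptions in Section 6.1 concern hospital admissions only. Section 6.7 adds that significant worsening on other safety assessments is also recorded as an AE or SAE.

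On SRT, the relevant sentence in Protocol Section 3.1 begins "The use of SRT (single episode) for disease progression for" and limits the use to three or fewer intracranial lesions. Section 4.5.2.1 likewise ties SRT to a single episode of intracranial progression. A secondary objective (Section 1.3.2) is intracranial-specific safety in "patients with or without stereotactic radiotherapy (SRT) received prior to study entry, or while on study".

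SAP 7.1.1 makes the AE summaries all-causality unless otherwise specified. SAP 7.6.5 states that "AEs will be summarized for all treated subjects and by cohorts and by SRT status"; 7.6.2 and 7.6.3 use the same split for SAEs and for AEs leading to discontinuation. None of these sections removes terms for progression.

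**The concern.** Growth of a brain metastasis, or a new one, is a change from the baseline scan and a worsening of a preexisting condition. If it is coded as an AE, one event counts both as lack of efficacy and as a safety event. In the overall all-causality totals this mixes toxicity with treatment failure.

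The by-SRT-status tables have a more specific problem. Subjects enter the on-study SRT group because they progressed in the brain. If that progression is itself an AE, the group starts with an event that owes nothing to SRT or to study drug. A reader of the any-AE or SAE line could take the resulting gap for toxicity of SRT combined with the regimen, which is the question the secondary safety objective asks. The split by SRT before study entry is fixed at baseline and is not selected in this way.

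**Working it through.** The plan states no figure on this point, so there is nothing to reproduce. The check is mainly a reading of the passages against one another.

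1. **Does the coding rule reach progression?** Section 5.3.3 has two filters: clinical significance, and the Section 6 criteria. Improvement on a scan fails the second. Progression passes it as worsening of a preexisting condition, whatever its cause. Progression judged to need SRT is hard to call clinically insignificant.

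2. **Is progression exempted elsewhere?** No exemption appears in Sections 6 to 6.7, or in SAP 7.1.1, 7.6.1 to 7.6.5 or 7.6.9.

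3. **Which tables does it reach?**
   - All-causality AE totals (SAP 7.6.5): yes, if the event falls on treatment or within 30 or 100 days of last dose (SAP 6.1.2, 7.1.1).
   - SAE and grade 5 tables: only if the event meets a Section 6.1 criterion such as death or hospitalization.
   - AEs leading to discontinuation (7.6.3): only if the action taken is recorded as drug discontinued (7.1.1).
   - Drug-related tables: only if the investigator marks progression as related, or causality is missing, which 7.1.1 counts as related.
   - Select AEs: Table 11-3 lists no progression terms.
   - Immune-mediated AEs (7.6.11): restricted to specific events considered potentially immune-mediated and, except for endocrine events, treated with immune-modulating medication.
   - Preferred-term rows: a progression term sits on its own line and can be read separately.

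4. **Scale of the artifact in the SRT split (illustration; all inputs assumed).** Let b be the share of subjects with at least one other AE, equal in both groups. Let q and p be the shares with progression coded as an AE in the window, with and without on-study SRT. Assume other AEs and coded progression are independent. Then

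   incidence = b + (1 − b) × q (or p), and gap = (1 − b)(q − p).

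   Take the limiting case q = 1, so the on-study SRT group shows 100%.

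| b | p | Without on-study SRT | Gap |
|---|---|---|---|
| 10% | 20% | 0.10 + 0.90 × 0.20 = 28% | 72 points |
| 60% | 50% | 0.60 + 0.40 × 0.50 = 80% | 20 points |
| 95% | 20% | 0.95 + 0.05 × 0.20 = 96% | 4 points |
| 95% | 50% | 0.95 + 0.05 × 0.50 = 97.5% | 2.5 points |

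The underlying difference is zero in every row. If almost every subject has some other AE, the any-AE line hides the problem. The same formula applies to SAEs, with b the rate of other SAEs and q and p counting only progression that meets a seriousness criterion, so q may be well below 1.

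**The case against.** The strongest reply is that the text is ambiguous rather than directive: clinical significance is a judgment, and the same section treats lesions as efficacy data. Handling of progression could also sit in text not available here (Section 3.4.2.2, Appendix 3) or in separate documents (core safety SAP, CRF completion guidelines, Data Presentation Plan). That cannot be ruled out. But Section 6 is the section that 5.3.3 cites for coding, and it has no exemption. An exemption elsewhere would still need reconciling with it.

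Several stronger readings are tempting and do not hold:

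- **Every progression is an SAE.** Section 6.1 says of pregnancy, overdose, "cancer, and potential drug induced liver injury (DILI) are not always serious by regulatory definition, these events must be handled as SAEs". The other listed items arise on study, whereas every subject enters with melanoma. Reading cancer as progression of that melanoma is strained.
- **Every progression is an AE leading to discontinuation.** That needs the action-taken entry. Disease progression is a separate discontinuation reason (SAP 7.3.1), and treatment may continue past progression (Protocol 4.5.7) or resume after SRT (4.5.2.1).
- **The on-study SRT group has 100% AE incidence by definition.** The safety window applies, and the clinical-significance judgment remains.
- **The number affected can be read from the design rate.** At 57/110, 110 − 57 = 53 subjects lack intracranial benefit. But that count includes non-evaluable subjects and deaths without a scan, and omits extracranial progression and later progression after benefit.

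It is also true that no test between SRT groups is planned, that MRI-defined edema, hemorrhage and pseudoprogression are summarized separately (Protocol 8.5.3), and that the on-study SRT group is selected after baseline and non-comparable however progression is coded. These points stand and narrow the concern. They do not remove the distortion of the total lines.

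**Conclusion.** The concern holds for the all-causality any-AE and SAE totals, mainly by on-study SRT status and to a lesser degree overall. As written, clinically significant progression belongs in the AE totals, and in the SAE and grade 5 totals when it meets a seriousness criterion. Subjects given SRT for intracranial progression within the window would generally carry such an event through selection.

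The size cannot be estimated from the documents, which give neither AE nor progression rates by SRT status. The illustrated gaps, 2.5 to 72 points, rest wholly on assumed inputs and the limiting case q = 1. They show that the effect depends strongly on how common other AEs are. The conclusion also assumes that sites follow 5.3.3 literally and that no exemption lies in the unseen text.

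No efficacy estimate is affected, and most of the detailed safety tables already separate toxicity from progression. This is a cheap improvement to the reading of one secondary safety objective.

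**What to change.** - **SAP 7.6.2 and 7.6.5:** repeat the overall and by-SRT-status all-causality totals excluding a list of MedDRA terms for progression of the study disease. Fix the list before final database lock. Keep complications such as edema, hemorrhage and seizure in the totals. Do the same in 7.6.3 if any progression event has drug discontinuation recorded as the action taken.
- **SAP, wherever the on-study SRT split is presented:** state that it is a post-baseline descriptive grouping that remains non-comparable even after the exclusion.
- **Protocol 5.3.3 and Section 6:** say whether progression of the study disease is to be recorded as an AE or SAE. This cannot be relied on to alter data already collected: SAP version 2.3 is dated 03 December 2020, after the interim database lock of 09 August 2020. The repeated tables therefore do the practical work.

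The cost is a term list and a few repeated tables, with no new data. If sites did not code progression as AEs, the repeated totals will match the planned ones, which is itself worth knowing.

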5.3.4 Pregnancy Testing

WOCBP are required to have several pregnancy tests performed as presented in [Table 5.1-1](#) to [Table 5.1-4](#). A negative serum or urine pregnancy test must be documented at the screening visit as per [Table 5.1-1](#). Additionally WOCBP must exhibit a negative serum or urine pregnancy test (minimum sensitivity 25 IU/L or equivalent units of HCG) within 24 hours prior to the start of study drug; therefore the screening pregnancy test may need to be repeated prior to the start of study drug dosing. A serum or urine pregnancy test will also be conducted at End of Treatment Visit.

5.3.5 ECOG Status

ECOG performance status will be evaluated at the screening evaluation and at each visit as outlined in Time and E. An outline of the ECOG performance status is provided in [Appendix 2](#).

5.3.6 Adverse Event Monitoring

Adverse Events (AEs) will be evaluated according to the NCI CTCAE Version 4.0 on a continuous basis starting from when the subject takes the first dose of study administration, up to and including Follow-Up and End of Treatment visits (at minimum, for 100 days following last dose of study drug). Serious Adverse Events (SAEs) must be collected from the time period following written consent to participate in the study up to and including follow-up.

5.3.7 Laboratory Test Assessments

Results of all safety laboratory collections must be obtained and reviewed in advance of study drug dosing, as applicable. Amylase and lipase should be collected with the chemistry collection, but these lab results do not require review prior to dosing.

Serum Chemistry is to be obtained as specified in [Table 5.1-1](#) to [Table 5.1-4](#). A free-T4 and free-T3 will be performed reflexively for out of range TSH values. A CBC with differential is to be obtained. The CBC with differential includes hemoglobin, hematocrit, white blood cells, platelets (direct platelet count), erythrocyte sedimentation rate, WBC differential enumeration of total and percentage of neutrophils, lymphocytes, eosinophils, basophils and monocytes.

